4.2.1.6 Reference-Based Multiple Imputation (MI)

Reference-based MI is an imputation model developed based on data from the placebo group only (Mallinckrodt, 2013). It will be the primary method of analysis for the secondary continuous endpoints which are part of the testing hierarchy, and will be also used for the components of the primary efficacy variable.

Reference-based multiple imputation assumes that the statistical behavior of the bimekizumab and placebo-treated study participants resembles that of the placebo-treated study participants in the study. All time points after discontinuation of the double-blind study treatment for both the bimekizumab and placebo groups will be considered missing. Multiple imputations will be used to replace missing outcomes for bimekizumab- and placebo-treated study participants who discontinued using multiple draws from the posterior predictive distribution estimated from the placebo arm, including intermittent missing data point. Missing Baseline values will however be imputed using data from all study participants. In the case of continuous endpoints, the procedure will be implemented as follows on the raw values:

- **Step 1:** Data will be processed sequentially, one timepoint (visit) at a time, by repeatedly calling SAS® PROC MI to impute missing outcome data at visits $t=1, \dots, \text{Week 16}$ (Week 16 being the time point of interest) using data from all study participants for imputation of missing baseline data and using data from the placebo-treated study participants arm only for imputation of missing post-baseline data.
 - **Step 1a:** Impute missing values at Baseline using an imputation model containing prior TNF α inhibitor exposure, region and the baseline visit based on all study participants.
 - **Step 1b (Initialization):** Set $t=1$ (Baseline visit).
 - **Step 1c (Iteration):** Set $t=t+1$. Create a dataset combining records from bimekizumab- and placebo-treated study participants with columns for covariates (prior TNF α inhibitor exposure and region) and outcomes at visits 1 to t . Outcomes for bimekizumab-treated

study participants with missing values at visit t are set to observed or previously imputed values at visits 1 to t-1. Bimekizumab-treated study participant with observed values at visit t are not included. Outcomes for placebo-treated study participants are set to observed at visit t or observed or previously imputed values at visits 1 to t-1. The outcomes should be sorted in chronological order in the model.

- **Step 1d (Imputation):** Impute missing values for visit t using previous outcomes for visits 1 to t-1, prior TNF α inhibitor exposure, and region. Note that only placebo data will be used to estimate the imputation model since no outcome is available for bimekizumab-treated study participants at visit t. As a consequence, the input dataset should include all study participants from placebo but only study participants from the bimekizumab arm that have values at timepoint t missing.
- **Step 1e:** Repeat steps 1a-1e for all timepoints, 100 times with different seed values (seeds ranging from 201 to 300) to create 100 imputed complete datasets. Study participants whose missing values were imputed in the last PROC MI call will be included in the input dataset for the next PROC MI call. Standard rounding rules will be applied to the imputed values. If the MI procedure yields a value outside of the pre-defined range for the given variable, the value will be updated to be within the predefined range of values for the endpoint of interest. For example, the imputed value for BASDAI will be updated to 0 or 10 in the case of an imputed value less than 0 or greater than 10, respectively (see [Table 4-2](#)).
- **Step 2:** The analysis will be done on the change from Baseline, and the model will be an ANCOVA model with treatment group, region, and prior TNF α inhibitor exposure as fixed effects and the Baseline value as covariate.

For generation of summary statistics, the 100 imputed datasets from Step 1 will be combined, and simple means and standard errors will be calculated using Rubin's rules (via SAS® PROC MIANALYZE). For calculation of other descriptive statistics (median, Q1, Q3, minimum and maximum), Rubin's rules do not apply. Multiple imputation estimates will be computed by calculating arithmetic means of the estimates from the multiple repetitions of the imputation algorithm. Thus, for median, Q1, Q3, minimum and maximum the following approach will apply:

- The data will be summarized by treatment, visit and imputation and the summary statistics will be computed.
- Results will be summarized by taking the mean value of each summary statistic at each visit across all imputations.
- The number of decimal places will remain the same as the original for display purposes (ie, if the mean was presented to 1 decimal place, the mean of the means will also be presented to 1 decimal place).

- **Step 3:** The results obtained from the 100 ANCOVA analyses in Step 2 (i.e. the Least Square Means for the treatment difference and the 95% CI for the contrasts) will be combined with Rubin's rules.

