2.4 Determination of sample size

Approximately 300 study participants will be randomly assigned in a 2:1 ratio to the following treatment groups: bimekizumab 160 mg sc (200 study participants) or placebo sc Q4W (100 study participants). The primary efficacy analysis is based on the bimekizumab dose versus placebo for ASAS40 response at Week 16. All sample size and power calculations were done at a significance level of 0.05 in a two-sided test.

All sample size and power calculations were performed using the software nQuery Advisor® 7.0.

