2.4.2 Power calculations for secondary endpoints in the hierarchical testing

The assumptions for power calculations of the secondary endpoints are based on the Week 12 results of AS0008, unless indicated otherwise. It was assumed that the treatment response at Week 12 and Week 16 would be the same (ie, conservative assumption). In addition, the observed data were adjusted in the same way as the primary endpoint to account for a higher number of study participants with prior TNF α inhibitor exposure and for a higher number of study participants with early withdrawal.

All power calculations for binary endpoints were performed using a 2-sided 2-sample Chi-square test with continuity correction (Fleiss et al, 1980). All power calculations for continuous endpoints were performed using a 2-sided 2-group Satterthwaite t-test (Moser et al, 1989). The power calculations provided below represent independent evaluations for each endpoint and do not account for multiplicity.

For ASAS40 response of the TNF α inhibitor-naïve population at Week 16, an ASAS40 response of 48% for the bimekizumab group was assumed. Placebo ASAS40 response at Week 16 is 18%. It is also assumed that 70% of the study participants in each treatment group are TNF α inhibitor-naïve. With those assumptions, the endpoint is powered with >99% at the planned sample size (ie, 140 and 70 study participants in the bimekizumab and placebo group, respectively).

For ASAS20 response at Week 16, an ASAS20 response of 70% for the bimekizumab group was assumed. Placebo ASAS20 response at Week 16 is 30%. With those assumptions, the endpoint is powered with 99% at the planned sample size.

For change from Baseline in BASDAI at Week 16, an adjusted between-treatment difference of -1.38 with an SD=1.8 for bimekizumab and SD=1.4 for placebo was used. With those assumptions, the endpoint is powered with >99% at the planned sample size.

For ASAS-PR at Week 16, an ASAS-PR of 17% for the bimekizumab group was assumed.

Placebo ASAS-PR at Week 16 was assumed to be 3.3%. With those assumptions, the endpoint is powered with 94% at the planned sample size.

For ASDAS-MI at Week 16, the ASDAS-MI data of AS0008 at Week 12 and Week 16 were used and the placebo response was extrapolated to Week 16. The assumed ASDAS-MI are 36.0% and 13.8% at Week 16 for the bimekizumab and placebo group, respectively. With those assumptions, the endpoint is powered with 98% at the planned sample size.

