For ASAS5/6 response at Week 16, an ASAS5/6 response of 44% for the bimekizumab group was assumed. Placebo ASAS-PR at Week 16 was assumed to be 5%. With those assumptions, the endpoint is powered with >99% at the planned sample size.

For change from Baseline in BASFI at Week 16, an adjusted between-treatment difference of -2.35 with an SD=1.9 for bimekizumab and placebo was used. With those assumptions, the endpoint is powered with >99% at the planned sample size.

For change from Baseline in nocturnal spinal pain at Week 16, the AS data from the certolizumab pegol study AS001 were used. An adjusted between-treatment difference of -1.88 with an SD=2.9 for bimekizumab and SD=2.4 for placebo was used. With those assumptions, the endpoint is powered with >99% at the planned sample size.

For change from Baseline in ASQoL score at Week 16, an adjusted between-treatment difference of -2.39 with an SD=4.5 for bimekizumab and placebo was used. With those assumptions, the endpoint is powered with >99% at the planned sample size.

For change from Baseline in PCS score of the SF-36 at Week 16, an adjusted between-treatment difference of 4.56 with an SD=8.1 for bimekizumab and SD=5.8 for placebo was used. With those assumptions, the endpoint is powered with >99% at the planned sample size.

For change from Baseline in BASMI at Week 16, an adjusted between treatment difference of -0.55 with an SD=0.8 for bimekizumab and SD=0.7 for placebo was used. With those assumptions, the endpoint is powered with >99% at the planned sample size.

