8.1.4.3 Analysis on individual components of ASAS40

The change from Baseline in each individual component of the ASAS40 response (PGADA, total spinal pain score, BASFI, and BASDAI) will be analyzed at Week 16 using an analysis of covariance (ANCOVA) model. The analyses for the component variable BASFI will be described in Section 8.2.2 where analyses for secondary endpoints are described. For all four variables, the model will include treatment, prior TNF α inhibitor exposure and region as fixed effects and the respective Baseline values as covariate. These analyses will be done on the RS and will explore the effect of the signs and symptoms of the individual components on the composite endpoint.

The following 4 attributes describe the estimand that will be used to define the treatment effect of interest for each of the four components for this analysis:

- Population = Study participants enrolled according to the protocol-specified inclusion/exclusion criteria and randomized to IMP
- Study participant level outcome = The change from Baseline in the ASAS component variable at Week 16
- Intercurrent event handling = An intercurrent event is defined as discontinuation of study treatment due to any reason prior to Week 16. This estimand targets the treatment difference in a scenario where withdrawal from study treatment does not occur, such that outcomes for study participants without an IE are as observed, and outcomes for study participants with an IE are treated as they had completed the randomized study treatment through Week 16 but on placebo. In that strategy, missing data and non missing data after IE (reset as missing) will be imputed using reference-based MI, in which the MI model is based on data from the placebo group.
- Population-level summary measure = the difference in the adjusted means between bimekizumab and placebo.

Intermittent missing data will be imputed using the reference-based MI method as well. See Section 4.2.1.6 for technical details on how the reference-based MI method will be implemented.

The SAS[®] PROC MIXED will be used to run the ANCOVA model.

For each ANCOVA model specified in this analysis, the following statistics will be presented:

- a) For placebo and bimekizumab: the adjusted least-square means (LSM) and standard error (SE)
- b) For the comparison between placebo and bimekizumab: the difference between the LSM, the associated 95% confidence intervals for the contrasts, and the corresponding p-value.

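### Three key continuous endpoints (and BASMI) are planned with a larger SD in the larger arm but analysed by ANCOVA with one pooled residual variance; on the SAP's own SDs the reported SEs are about 5% to 11% too large, on the conservative side

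*SAP*

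**What the plan says.** Section 2.4 plans 2:1 allocation, "bimekizumab 160 mg sc (200 study participants) or placebo sc Q4W (100 study participants" in the SAP's words, and works at the usual level: "All sample size and power calculations were done at a significance level of 0.05 in a two-sided test".

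Section 2.4.2 names the sizing test: "All power calculations for continuous endpoints were performed using a 2-sided 2-group Satterthwaite t-test". That test keeps a separate variance for each arm, and the planning SDs use this freedom:

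- BASDAI: "an adjusted between-treatment difference of -1.38 with an SD=1.8 for bimekizumab and SD=1.4 for placebo was used".
- Nocturnal spinal pain: "An adjusted between-treatment difference of -1.88 with an SD=2.9 for bimekizumab and SD=2.4 for placebo was used".
- SF-36 PCS: "an adjusted between-treatment difference of 4.56 with an SD=8.1 for bimekizumab and SD=5.8 for placebo was used".
- BASMI: difference -0.55, SD 0.8 against 0.7.
- BASFI (SD 1.9) and ASQoL (SD 4.5): the same SD in both arms.

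The analysis is fixed elsewhere. Section 4.2.1.6, Step 2: "The analysis will be done on the change from Baseline, and the model will be an ANCOVA model with treatment group, region"; the sentence goes on to prior TNFα inhibitor exposure and the Baseline value. Section 4.2.1.7 gives the same model for the hypothetical estimand. Section 8.1.4.3 names the procedure ("PROC MIXED will be used to run the ANCOVA model"), and Section 8.2.2 carries that model to the secondary continuous endpoints. None of these sections mentions a residual variance by arm, a robust standard error or a degrees-of-freedom method.

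**The concern.** An ANCOVA described only by its fixed effects and a covariate has a single residual variance. The SAP does not write out a common-variance assumption, but this is what the stated model fits.

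With equal arms, pooling unequal variances does little harm to the standard error of a difference. At 2:1 it matters. The pooled variance is dominated by the larger arm. If that arm is also the more variable one, its high variance is applied to the 100 placebo participants too, and the standard error comes out too large.

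The SAP's planning figures describe exactly this situation for BASDAI, nocturnal spinal pain, SF-36 PCS and BASMI. At stake are the reported standard errors, 95% confidence intervals and p-values, which would not have their nominal properties under the trial's own assumptions.

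**Working it through.** **Inputs.** n1 = 200 (bimekizumab), n2 = 100 (placebo), two-sided 0.05, from Section 2.4; differences and SDs from Section 2.4.2.

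**Step 1: reproduce the stated power.** With SE = sqrt(s1²/200 + s2²/100), Satterthwaite degrees of freedom and the noncentral t distribution, power is above 99.99% for BASDAI and BASFI, 99.996% for nocturnal spinal pain, 99.07% for ASQoL, 99.98% for SF-36 PCS and 99.998% for BASMI. The SAP's figure of more than 99% for each is confirmed.

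**Step 2: standard error under each variance assumption.**

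- Separate variances: SE_sep = sqrt(s1²/200 + s2²/100).
- Pooled variance: SE_pool = sqrt(V × (1/200 + 1/100)), with V = (199 s1² + 99 s2²)/298.

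SF-36 PCS in full: SE_sep = sqrt(65.61/200 + 33.64/100) = sqrt(0.66445) = 0.815. V = (199 × 65.61 + 99 × 33.64)/298 = 54.99, so SE_pool = sqrt(54.99 × 0.015) = 0.908. Ratio 0.908/0.815 = 1.114.

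| Endpoint | SE_sep | SE_pool | SE ratio | 95% CI half-width, separate → pooled | Actual type I error, pooled |
|---|---|---|---|---|---|
| SF-36 PCS | 0.815 | 0.908 | 1.114 | 1.605 → 1.787 (+11.4%) | 0.028 |
| BASDAI | 0.1892 | 0.2055 | 1.086 | 0.373 → 0.404 (+8.5%) | 0.033 |
| Nocturnal spinal pain | 0.316 | 0.336 | 1.065 | 0.622 → 0.661 (+6.3%) | 0.036 |
| BASMI | 0.0900 | 0.0941 | 1.045 | 0.177 → 0.185 (+4.4%) | 0.040 |
| BASFI, ASQoL | – | – | 1.000 | -0.2% (degrees of freedom only) | about 0.05 |

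The type I error is 2 × [1 − Φ(t × SE ratio)], where t is the 97.5% point of t with 298 degrees of freedom.

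**Step 3: power under the pooled model.** It stays above 99% for all six endpoints. For SF-36 PCS, the worst ratio, it is 99.97% against 99.98% with separate variances.

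**Step 4: does covariate adjustment remove the effect?** The SAP does not say how much variance Baseline explains, so 0%, 20% and 40% of the placebo variance were assumed. A common-variance ANCOVA with Baseline, prior TNFα inhibitor exposure and region was simulated 4,000 times per setting. Mean reported SE over true SE was 1.11 to 1.14 for SF-36 PCS, 1.10 to 1.13 for BASDAI, 1.06 to 1.09 for nocturnal spinal pain and about 1.05 for BASMI (Monte Carlo error about 0.01). Adjustment does not remove the effect.

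**The case against.** The strongest reply is that there is no contradiction. Section 2.4.2 names a test for power only. The SAP also sizes its binary endpoints with a continuity-corrected chi-square test and analyses them by adjusted logistic regression, so a sizing test simpler than the final model is its normal practice. This stands: the sizing test does not bind the analysis. What remains is that the SAP's own SDs predict a miscalibrated standard error from the model chosen, and no section provides for it.

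The second reply concerns scope. Section 8.2.2 puts BASMI outside the testing hierarchy with a nominal p-value and reserves reference-based imputation for hierarchy endpoints. The SAP is not consistent here: Section 2.4.2, headed as covering endpoints in the hierarchical testing, powers BASMI; the legend to Figure 4-1 lists it; and Section 8.2.2 counts 11 key secondary endpoints, although the 13 in Section 2.2.1.2 less the three it excludes leave 10. On either reading BASMI gets the same ANCOVA, through 4.2.1.6 or 4.2.1.7. The firm claim on key endpoints covers three of the five continuous endpoints certain to be in the hierarchy.

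The third reply is that the percentages are firmer than their inputs. The SDs are planning values, mostly Phase 2b Week 12 results and, for nocturnal spinal pain, from a study of another drug. The reported interval also includes between-imputation variance from 100 data sets, which enters both versions. This stands as well: the ratios are complete-data figures, not forecasts of the final intervals.

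**Conclusion.** The point holds, at low severity. On the planning SDs, the common-variance ANCOVA reports standard errors about 11%, 9%, 6% and 5% too large for SF-36 PCS, BASDAI, nocturnal spinal pain and BASMI. This assumes that the residual SDs keep the planning ratio, and it leaves out between-imputation variance.

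A reader might infer three stronger things that the document does not support.

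- **That error control or the sample size is at risk.** The direction is conservative and power stays above 99%, so no test decision is foreseeably affected on these figures.
- **That precision is lost, as if participants were discarded.** For SF-36 PCS one could compute 1 − (0.815/0.908)² = 19%. But the treatment difference is essentially the same difference in arm means under either model, so its sampling variance hardly changes. Only the reported uncertainty is inflated.
- **That the tests may be anti-conservative.** That would need placebo to be the more variable arm. Every SD pair in Section 2.4.2 is larger on bimekizumab or equal, so the SAP gives no ground to expect it. An arm-specific variance would nevertheless protect against that case too.

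**What to change.** In Sections 4.2.1.6 (Step 2), 4.2.1.7 (Step 4) and 8.1.4.3, state that the residual variance may differ by treatment arm (PROC MIXED with REPEATED / GROUP=treatment), with Satterthwaite or Kenward-Roger degrees of freedom, fitted in each imputed data set before the results are combined by Rubin's rules. A robust standard error, with its degrees-of-freedom rule also stated, would serve as an alternative. Section 8.2.2 then inherits the change by its cross-reference. The cost is one sentence in the SAP, one program option and one extra variance parameter. If the arm variances prove equal, as planned for BASFI and ASQoL, the results will barely differ from those of the present model.

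Separately, make Section 2.4.2, the Figure 4-1 legend and Section 8.2.2 agree on whether BASMI belongs to the testing hierarchy.

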4.2.1.7 Hypothetical Estimand - Multiple Imputation (MI)

For secondary continuous efficacy endpoints, the methods described above in Steps 1 to 5 of Section 4.2.1.4.1 for the non-composite binary endpoints will apply based on the values at the timepoint of interest, with the following differences:

- The intercurrent event is study treatment discontinuation due to any reason and the IE date is as defined in Section 3.4.
- Step 3 is not relevant for continuous endpoints.
- In Step 4 (**Excluding hs-CRP**), the 100 imputed datasets from Step 2 will be combined, and simple means and standard errors will be calculated using Rubin's rules (via SAS® PROC MIANALYZE). For calculation of other descriptive statistics (median, minimum and maximum), Rubin's rules do not apply. Multiple imputation estimates will be computed by calculating arithmetic means of the estimates from the multiple repetitions of the imputation algorithm. Thus, for median, minimum and maximum the following approach will apply:
 - The data will be summarized by treatment, visit and imputation and the summary statistics will be computed.
 - Results will be summarized by taking the mean value of each summary statistic at each visit across all imputations.
 - The number of decimal places will remain the same as the original for display purposes (ie, if the mean was presented to 1 decimal place, the mean of the means will also be presented to 1 decimal place).
- In Step 4 **for hs-CRP only**: The CRP data will be presented using the geometric mean, median, Q1, Q3, minimum and maximum. The change from Baseline will be expressed as the ratio to Baseline in the by-visit summaries. The following approach will be applied:
 - Any imputed CRP values $<0.5^*LLOQ$ (0.1) will be reset to 0.05
 - The natural logarithm of the absolute values will be calculated
 - The change from Baseline (based on logged values) will be calculated
 - The change from Baseline (based on logged values) will be summarized by treatment, visit and imputation
 - The datasets will be combined using PROC MIANALYZE in order to get the mean for the absolute values and change from Baseline (based on logged data) across imputations
 - The estimates of the mean for the absolute values and changes from Baseline will be back-transformed to obtain the geometric mean on the original scale. This back-transformation of the mean change from Baseline (based on logged data) gives the geometric mean ratio to Baseline (on the original scale).
 - For the median, Q1, Q3, minimum and maximum the procedure outlined above for the other endpoints will be followed (based on logged values). And the resulting summary statistics will finally be back-transformed to obtain the values on the original scale.

- In Step 4, the analysis will be done on the change from Baseline, and the model will be an ANCOVA model with treatment group, region, and prior TNF α inhibitor exposure as fixed effects and the Baseline value as covariate.
- In Step 5, the results obtained from the 100 ANCOVA analyses in Step 4 (ie, the Least Square Means for the treatment difference and the 95% CI for the contrasts) will be combined with Rubin's rules.

For other continuous efficacy endpoints, the following steps will apply:

- The same Steps 1 to Step 5 as the ones described for non-composite binary efficacy endpoints (but excluding Step 3) will be implemented.
- For ASDAS-CRP endpoint only, the following should also be considered:
 - after each MCMC and monotone steps to account for potentially different LLOQs across individuals: any imputed CRP values $<0.5 * \text{the LLOQ (0.1)}$ will be reset to 0.05.
 - any imputed CRP values <2 will be rest to 2 only one time after monotone regression imputation step and immediately prior to calculation of the component score.
- The same Step 4 and Step 5 as those described above for secondary endpoints (but excluding the “Step 4 for hs-CRP only”) will be implemented.

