- Percentages will be based only on those study participants with observed data for the variable being summarized. As the denominator may be different from the number of study participants in the analysis set being considered, the denominator should be displayed in the table. The general format for displaying this will be “n/Nsub (%).”

The approach to be considered will be further specified in the relevant section of the variable of interest.

Unless otherwise noted, all percentages will be displayed to one decimal place. No percentage will be displayed for zero counts, and no decimal will be presented when the percentage is 100%.

Unless stated otherwise, continuous endpoints will be expressed as a change from Baseline which will be calculated as the value at a specific timepoint minus the value at Baseline.

For continuous parameters, descriptive statistics will include number of study participants with available measurements (n), arithmetic mean, standard deviation (SD), median, minimum, and maximum (unless otherwise stated).

For hs-CRP variable, the summary statistics should contain arithmetic mean, geometric mean, geometric coefficient of variation (CV), median, first and third quartile (Q1 and Q3), minimum and maximum. The geometric CV (%) will be calculated using the following formula:

$$CV = \sqrt{e^{SD_{ln}^2} - 1}$$

where SD_{ln} represents the standard deviation of the ln-transformed hs-CRP values.

For bimekizumab PK concentrations, geometric mean, geometric CV, 95% confidence intervals for geometric mean (assuming log-normally distributed data) will be calculated if at least 2/3 of the values of interest are above the LLOQ and $N \geq 3$. If this is not the case, only median, minimum and maximum will be presented.

Decimal places for descriptive statistics will always apply the following rules:

- “n” will be an integer.
- Mean, SD, SE, and median will use 1 additional decimal place compared to the original raw value from the Case Report Form (CRF).
- Coefficient of variance (CV [%]) will be presented with 1 decimal place.
- Minimum and maximum will have the same number of decimal places as the original raw value.

If the number of decimal places reported in the raw data is varied then either the maximum raw number of reported decimal places or 3 will be used, whichever is the lowest, as a guide for the descriptive statistics.

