8.2.3 Additional statistical analysis of selected secondary efficacy variables

For the “change from Baseline in MASES index at Week 16 in the subgroup of study participants with enthesitis at Baseline”, and for the “enthesitis-free state at Week 16 based on the MASES Index in the subgroup of study participants with enthesitis at Baseline” secondary efficacy variables, additional statistical tests and calculation of inferential statistics will be performed. As these tests are not part of the multiplicity-controlled procedure, the associated p-values are considered nominal and are not controlled for multiplicity.

For the enthesitis-free state responder variable, the logistic regression model described in Section 8.1.2 will be used for analysis. The p-values will be based on the conditional logistic regression model to test general association. Missing values will be imputed using the NRI.

For the MASES continuous variable, the Hypothetical Estimand approach used for other continuous variables will be applied based on the ANCOVA model describe in Section 4.2.1.7 and Section 8.2.2.

The results of these inferential statistics will be presented in a single table summarizing the estimates (OR for the binary endpoint, LSM for the continuous endpoint) with their 95% CI and the associated p-values. The results will be pooled with the results obtained for selected other efficacy variables (see Section 8.3.3).

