8.3.3 Additional statistical analysis of selected other efficacy variables

Although statistical testing is not planned for other efficacy variables per protocol, statistical testing and inferential statistics are of interest for selected endpoints. As these tests are not part of the multiplicity-controlled procedure, the associated p-values are considered nominal and should not be used for inference. Similarly as described in Section 8.2.3, statistical tests and calculation of inferential statistics will be performed for the following selected other efficacy endpoints:

- ASAS40 at Week 1, Week 2, Week 4, Week 8, Week 12
- ASAS40 in the TNF alpha inhibitor-naïve study participants at Week 1, Week 2, Week 4, Week 8, Week 12
- ASAS20 at Week 1, Week 2, Week 4, Week 8, Week 12
- PGADA at Week 1, Week 2, Week 4, Week 8, Week 12, Week 16
- Total spinal pain at Week 1, Week 2, Week 4, Week 8, Week 12, Week 16
- Nocturnal spinal pain at Week 1, Week 2, Week 4, Week 8, Week 12
- BASFI at Week 1, Week 2, Week 4, Week 8, Week 12
- Mean BASDAI Q5 and Q6 score at Week 1, Week 2, Week 4, Week 8, Week 12, Week 16
- BASDAI at Week 1, Week 2, Week 4, Week 8, Week 12,
- BASDAI50 at Week 1, Week 2, Week 4, Week 8, Week 12, Week 16
- CRP at Week 1, Week 2, Week 4, Week 8, Week 12, Week 16
- ASDAS-CRP at Week 16
- MASES at Week 16
- Enthesitis free state at Week 16
- TJC at Week 16
- SJC at Week 16
- FACIT-Fatigue at Week 16
- WPAI at Week 16
- ASspiMRI at Week 16
- SPARCC at Week 16

The same models as described in Section 8.2.3 will be run, and results will be presented in one single table together with the results for secondary endpoints.

In addition, the Week 16 results from the primary analysis for the primary endpoint ASAS40, and key secondary endpoints in the hierarchy (ASAS20, BASDAI, BASFI, nocturnal spinal pain) will also be included in this table.

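### The SAP contradicts itself on the scale of the hs-CRP ANCOVA at six visits: the literal text gives an arithmetic change, while the by-visit CRP results are ratios to Baseline

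*SAP*

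**What the plan says.** Four places in the SAP together determine how CRP is tested.

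- Section 8.3.3 lists "CRP at Week 1, Week 2, Week 4, Week 8, Week 12, Week 16" and adds that "The same models as described in Section 8.2.3 will be run". It also says that "the associated p-values are considered nominal and should not be used for inference".
- Section 8.2.3 handles its continuous variable, MASES, as follows: "the Hypothetical Estimand approach used for other continuous variables will be applied based on the ANCOVA model describe in Section 4.2.1.7". The output is an LS mean estimate with a 95% CI and a p-value.
- Section 4.2.1.7 gives the model: "In Step 4, the analysis will be done on the change from Baseline, and the model will be an ANCOVA model". The Baseline value is the covariate. No scale is named, and hs-CRP is not treated separately in this bullet.
- Section 3.1 defines change, unless the SAP says otherwise, as "the value at a specific timepoint minus the value at Baseline".

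Section 4.2.1.7 also contains a version of Step 4 written for hs-CRP alone. It takes natural logs, forms the change on the log scale and back-transforms to a geometric mean ratio to Baseline. It stands under the instructions for secondary continuous endpoints. For other continuous endpoints the section then calls for "The same Step 4 and Step 5 as those described above for secondary endpoints (but excluding the", and the item excluded is that hs-CRP version of Step 4. Section 2.2.1.3 lists hs-CRP as an other variable; it is not among the secondary variables in 2.2.1.2. Sections 8.3.1.5 and 8.3.2 show hs-CRP by visit as a ratio to Baseline.

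**The concern.** Read literally, the log step is assigned to a class of endpoints that does not contain hs-CRP and withheld from the class that does. It therefore applies to no endpoint at all. That makes it a defective rule, more than an omitted detail.

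Two programmers could reasonably fit different models for six pre-listed tests and get different estimates and p-values. If the arithmetic reading is used, the between-group result is a difference in mg/L, while the by-visit table for the same variable reports ratios. A few high values would carry much of the weight in the LS means, so the comparison would be less precise than the log-scale analysis that the SAP's own convention for CRP suggests.

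**Working it through.** **Which scale does the text give?** Following the references in order:

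1. 8.3.3 sends CRP to the models of 8.2.3.
2. 8.2.3 sends continuous variables to the ANCOVA of 4.2.1.7.
3. That ANCOVA is on change from Baseline, with no hs-CRP exception.
4. The 3.1 default makes change an arithmetic difference.
5. The only log-scale text is the hs-CRP version of Step 4. It is written for summaries, ends in a within-group ratio, and is excluded for other continuous endpoints.

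The literal result is CRP(t) − CRP(0) with CRP(0) as covariate.

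**What would that cost?** The SAP states no SD, effect size or power for CRP, so there is no figure of its own to reproduce. The cost was simulated.

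Inputs from the SAP: 200 and 100 participants (section 2.3), two-sided 0.05 (section 3.1), and a floor of 0.05 mg/L (section 4.2.1.7).

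Assumed inputs: lognormal CRP with Baseline geometric mean 7 mg/L; the same SD of ln CRP at both visits, 0.5 to 1.4; Baseline-to-visit correlation on the log scale 0.3, 0.5 or 0.7; placebo ratio to Baseline 0.95; treatment ratio of geometric means (GMR) 0.4, 0.6, 0.7 or 0.8. There were no missing data and no stratification terms. Each setting used 1,000 simulated trials, so the Monte Carlo standard error of a power figure is at most √(0.25/1000) = 1.6 percentage points.

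Models compared:

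- Untransformed: CRP(t) − CRP(0) = a + b·treatment + c·CRP(0) + error
- Log: ln CRP(t) − ln CRP(0) = a′ + b′·treatment + c′·ln CRP(0) + error, where exp(b′) is the treatment ratio of geometric means

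Relative efficiency (RE) = (mean t, untransformed ÷ mean t, log)². Loss = 1 − RE.

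Results at correlation 0.5:

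| SD of ln CRP | RE over GMR 0.4–0.8 | Loss | Power at GMR 0.7, untransformed | Power at GMR 0.7, log |
|---|---|---|---|---|
| 0.5 | 0.803–0.910 | 9.0–19.7% | 100% | 100% |
| 0.7 | 0.700–0.799 | 20.1–30.0% | 98.3% | 99.8% |
| 0.8 | 0.651–0.726 | 27.4–34.9% | 93.1% | 99.0% |
| 1.0 | 0.550–0.596 | 40.4–45.0% | 69.8% | 89.7% |
| 1.2 | 0.456–0.494 | 50.6–54.4% | 49.2% | 79.2% |
| 1.4 | 0.375–0.403 | 59.7–62.5% | 34.3% | 66.6% |

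As a rough check of one cell (SD 1.2, GMR 0.7), the median t statistics are −1.940 and −2.743, and (1.940/2.743)² = 0.50, close to the mean-based 0.487.

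Over the whole grid, RE runs from 0.930 (SD 0.5, correlation 0.3, GMR 0.6) to 0.309 (SD 1.4, correlation 0.7, GMR 0.4), a loss of 7% to 69%. For a large effect (GMR 0.4), untransformed power is at least 92.9% everywhere.

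Type I error at correlation 0.5, with 5,000 trials for each SD (0.8, 1.0, 1.2, 1.4): untransformed 5.0%, 5.3%, 4.3%, 4.6%; log 5.3%, 5.2%, 5.1%, 5.0%. Both are close to nominal.

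**The case against.** The strongest reply is that the SAP nowhere says that CRP is to be tested untransformed or in mg/L. The arithmetic definition in 3.1 is only a default. For hs-CRP, sections 4.2.1.7, 8.3.1.5 and 8.3.2 depart from it, and the ANCOVA bullet belongs to the same Step 4 as the log-change bullets. A sensible programmer might carry the log change into the model, and might take the exclusion as aimed at the remaining endpoints or at ASDAS-CRP, which is discussed just above it. This stands to the extent that a reader who infers a deliberate choice of the mg/L scale goes beyond the text. It does not remove the contradiction, because the intended reading has to overrule both the default and the exclusion.

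A reader might also infer that the p-value is detached from its own estimate. It is not: under 8.2.3 the LS mean, CI and p-value come from one model on one scale. The mismatch is between that table and the by-visit ratios. Nor is every CRP summary geometric, since section 3.1 also asks for the arithmetic mean, median and quartiles.

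Section 8.3.1.5 sets CRP values of 500 mg/L or more to missing before imputation. This limits gross outliers but not ordinary skewness. Under the assumptions above at SD 1.4, 500 mg/L lies ln(500/7)/1.4 = 3.05 SDs above the Baseline mean of ln CRP, a point that about 0.1% of values exceed.

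Finally, the tests are nominal and, by the SAP's own words, not for inference. That stands in full and limits the importance of the point.

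**Conclusion.** The point holds as a minor one. The scale of the hs-CRP ANCOVA is contradictory; the literal reading is the arithmetic change, and the exclusion in 4.2.1.7 leaves the log step with no endpoint to apply to. On the literal reading the test keeps its type I error, so it is not invalid. The cost is precision and a result that cannot be set directly beside the ratios shown elsewhere.

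A reader might conclude that half or more of the information is lost. The documents do not support that as a general statement, because they give neither the SD of ln CRP nor the correlation. Under the assumed lognormal model the loss is 7% to 69%; at correlation 0.5 it passes half only at an SD of about 1.2 or more. For a large CRP effect the power difference is small. No primary, key secondary or other confirmatory conclusion is affected.

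**What to change.** In sections 4.2.1.7 and 8.3.3, state that hs-CRP is analysed as change from Baseline in ln(CRP), with ln(Baseline CRP) as covariate and the same factors as the other ANCOVAs. The treatment difference and its 95% CI, pooled over imputations on the log scale, should be exponentiated and reported as a ratio of geometric means.

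Reword the exclusion in 4.2.1.7 so that the hs-CRP version of Step 4 applies to hs-CRP and is skipped only for the remaining other continuous endpoints. Label the CRP rows of the 8.3.3 table as ratios, since the neighbouring continuous rows are differences.

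The cost is a few sentences of SAP text, one log transformation and one back-transformation in the program, and a table footnote. No data collection changes.
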